1. STUDY DESIGN

The study design was chosen according to the current standards required by ISO, GCP and according to national requirements.

- a. A Parallel-Arm, Statistician, Operator and Examiner are blinded, RCT will be established;
- b. The RCT will be run as mono-center;
- c. A total of 44 subjects will be recruited to participate in the study. It is expected that all of 40 subjects will complete the study in total;
- d. Admission into the study will be via rolling admission (estimated recruitment time: 12 months);
- e. Each subject must have at least 2 residual sites/pockets with probing depth ≥ 6 mm or pockets of 5 mm with bleeding on probing in two different quadrants;
- f. Each subject will follow the following treatment protocol:
 - i. – Visit 1 (Screening): (within 29 days prior to baseline) – consent secured; screening and entry into study; baseline data collection; full periodontal charting (full-mouth PD, REC, BOP, PI); identification the sites for microbiological sample.
 - ii. – Visit 2 (T0 – Baseline Visit+Treatment): collection of microbiological samples from the two deepest sites in two different quadrants. All patients receive a full mouth periodontal treatment (GBT) and OHI (oral hygiene instruction). According to the list of randomization the patient will be allocated into one of the two arm of probiotic treatment: study lozenges are given to all patients to consume at home. The patients are instructed to dissolve these on their tongue twice a day, preferably after brushing, for 3 weeks. The patients of the probiotic group will receive probiotic lozenges containing *Lactobacillus reuteri* DSM 17938 and *Lactobacillus reuteri* ATCC PTA 5289 (a minimum of 2×10^8 colony-forming units L. reuteri Prodentis/lozenge, BioGaia AB). The patients of the control group will receive control lozenges without live bacteria. Furthermore, the probiotic and control lozenges will be identical in taste, texture and appearance.
 - iii. – Visit 3 (T1) – 3 weeks: the participants will be asked to return the empty packages of the study medication to examine the adherence. At that time, side effects will also be questioned by the examiner by means of an open question. Collection of the

microbiological sample will be performed from the same subgingival sites as during Baseline (T0) and reinforcement of OHI.

iv. – Visit 4 (T2) - 3 months: Collection of the microbiological sample from the same subgingival sites as during Baseline (T0), collection of full periodontal charting (PD, REC, PI, BOP) and reinforcement of OHI.

v. – Visit 5 (T3) - 6 months: Collection of the microbiological sample from the same subgingival sites as during Baseline (T0), collection of full periodontal charting (PD, REC, PI, BOP) and full mouth GBT will be done in both groups. Subjects will either be entered into a routine recall system for treatment or scheduled for any further periodontal treatment as clinically indicated, and exit the study.

- g. All treatments are made by the same clinician;
- h. Calibration: the examiner is calibrated showing an intra-examiner reproducibility of 96% for duplicate measurement of probing pocket depth (PPD) with a maximum difference of 1 mm in 5 patients;
- i. Data collection: A PCP-UNC 15 periodontal probe is used on six sites per tooth (mesio-buccal, buccal, disto-buccal, mesio-lingual, lingual and disto-lingual) with a gentle probing force by the same clinician. Measurements are rounded to the nearest millimeter;
- j. Clinical assessment data will be recorded via hard copy CRFs. CRFs will be submitted to a data entry staff member for entry into the statistical database. At the conclusion of the study, such statistical database will be submitted to the statistician for the preparation of the statistical analysis and the final study report.

2. TREATMENTS

Study lozenges (both: test and placebo) will be delivered to the study center prior study start.

Specification of test treatment – Microbiological analysis

Microbiological analysis will assess changes in microbial composition and the proportion of sequences assigned as *Lactobacillus reuteri* in subgingival plaque samples.

Sample for microbiological analysis:

1. Subgingival plaque collection

Subgingival plaque from 2 sites with probing depth ≥ 6 mm or pockets of 5 mm with bleeding on probing in two different quadrants (the two deepest sites) will be collected using sterile paper point.

After isolating the site with cotton rolls, supragingival plaque was removed using a Gracey curette and the site was dried with airflow. Subsequently, two paper points were inserted in the pocket for 10 s. The paper points with subgingival plaque will be placed in empty sterile Eppendorf vial and stored on ice until transport to the laboratory (max 2 h), and stored at -80°C.

1. Sample processing

Samples will be shipped on dry ice to the Department of Preventive Dentistry, at the Academic Centre for Dentistry Amsterdam (ACTA). Bacterial DNA will be extracted, purified and quantified and prepared for 16S rRNA gene amplicon sequencing using Illumina MiSeq technology. The obtained sequencing reads will be quality filtered and processed into zero radius operational taxonomic units (zOTUs) and assigned taxonomy using HOMD database.

The zOTU-table will be randomly subsampled to even depth. The Shannon diversity index per sample will be calculated using dedicated software (PAST). This diversity index will be used to characterize the diversity of the microbial community and accounts for both the abundance and evenness of the OTUs present in the sample. Data ordination plots will be obtained using the Principal Component Analysis (PCA) on the \log_2 transformed zOTU-data. The statistical difference in microbial profiles between the study groups at each time point will be assessed using permutational analysis of variance (PERMANOVA) with Bray-Curtis similarity distance. Metagenomic biomarker discovery tool LEFSE will be used to identify microbial taxa that significantly discriminate the groups. The Bray-Curtis similarity index will be calculated between the dependent samples collected at different time points and the similarity distances between the study groups will be compared statistically.

zOTUs that taxonomically will be assigned to genus *Lactobacillus*, will be analyzed separately, in order to assess if the probiotic strains have established in the oral cavity. For this, first, a phylogenetic tree will be created based on the representative sequence of each zOTU. Sequences that will be phylogenetically related to *L. reuteri* 16S rRNA gene fragment amplified, will be marked as potential probiotic sequences. Relative abundances of all genus lactobacillus sequences and *L. reuteri* sequences between groups per timepoint will be compared.

Concomitant Therapy

A necessary concomitant medication or therapy is permitted as long as it is not excluded in the exclusion criteria. Every medication has to be reported in the CRF (Appendix 1) and in the

Concomitant Medication form (Appendix 2). All changes during the study are to be reported in the CRF. Usage of prohibited therapy will lead to the exclusion of the subject.

Blinding and Randomization

Blinding: The statistician will be blinded to the group identification. The patient and the operator will not know the treatment. Knowledge of the randomization list will be limited to the persons responsible for creation of the randomization list, provider of randomization numbers to study site, and delivery of the test/control treatment until the last subject (i.e. final examination of the last subject), quality control and verification of the CRFs is completed.

Randomization and allocation concealment: The randomization of the study protocols will be performed by a staff member who is not further involved in this study. This will be done based on a computer-generated table (www.randomization.com) that links each patient to one of the treatment groups. The same staff member will be responsible for blinding the study products. This will be done by labelling the packaging of these products with a letter indicating the treatment group. Additionally, the jars containing the lozenges will be identical in appearance and non-transparent. When a patient will be included in the study, the study medication will be handed out to the researcher according to group to which that patient will be assigned based on the patient number and the randomization list. The similarity of the packaging, and the identical appearance, texture and taste of the study products make the double-blinding of the researcher and patient possible.

Implementation: The Principal Investigator will be informed immediately of Serious Adverse Events (SAEs), regardless of the causality relationship between the administration of the investigational treatment and the SAE.

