Under the direct supervision of the Principal Investigator, certain duties may be delegated during the course of the study. These responsibilities will be documented on the transfer of responsibilities form maintained in the Investigator Site file.

The **Statistician** will be responsible for:

- sample size calculation;
- statistical plan;
- statistical section of the protocol;
- statistical evaluation;
- final statistical report.

The **Microbiologist** will be responsible for:

- sample microbiological processing and analysis;
- final microbiological report.

OBJECTIVE

The study will be performed to assess the efficacy of the addition of *Lactobacillus reuteri* containing lozenges in the supportive therapy of periodontitis in terms of reduction of PD (Probing Depth).

INTRODUCTION

Probiotics are defined as 'live microorganisms which, when administered in adequate amounts, confer a health benefit on the host'. The influence of probiotics on pathogens flora can derive from three principal modes of action: innate and acquired host defense modulation, production of antibacterial substances and competitive exclusion mechanism. In particular, *Lactobacillus reuteri* has been studied for its antibacterial and anti-inflammatory properties.

It is a heterofermentative bacterium and the distinct strains have different characteristics. In particular it acts as an antibiotic, induces oxidative stress on pathogens, is resistant to proteolytic and lipolytic and present anti-inflammatory properties.

Literature pointed out to potential effectiveness of *L. reuteri* as an adjunct to non-surgical periodontal therapy in initial treatment of periodontitis patients but underlined the limits of their conclusions due to the heterogeneity of the studies and to the few patients included. There is thus a need for more long-term randomized controlled studies. In particular, only one study addressed the use of this probiotic during the supportive therapy and in particular in patients with severe forms of periodontitis but few patients were included.

Patients meeting the criteria of periodontitis stage III and IV, grade C are considered to be affected by severe and advanced forms of periodontitis with a rapid rate of progression. This group of patients could particularly benefit from supplements in the maintenance of periodontal health.

STUDY OUTCOMES

- a. Primary outcome measure: change in PD
- b. Secondary outcomes:

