 - changes in the following clinical parameters: Pocket closure, REC (Clinical Gingival Recession), CAL (Clinical Attachment Level), BOP (Bleeding on Probing), PI (Plaque Index).
 - Risk progression of the periodontitis and the need of periodontal surgery.
- c. Microbiological outcomes: changes in microbial composition and proportion of sequences identified as *Lactobacillus reuteri* in the deepest residual pockets.

STUDY POPULATION

Forty-four (44) adults, aged 18-75 years, will be entered into study (randomized). It is expected that forty (40) subjects will complete the study.

Randomized subjects who deviate from the protocol (major protocol deviation) and, for this reason, are excluded from the analysis, will be replaced to guarantee that the sample required for the analysis (40) is reached.

Patients will be treated at the Department of Surgical Specialities Radiological Science and Public Health, School of Dentistry, Section of Periodontics, Brescia, Italy from 04/2020.

Inclusion Characteristics

- Signed Informed Consent Form.
- Male and female subjects, aged 18-75 years, inclusive.
- Good general health (free of systemic diseases such as diabetes, HIV infection or genetic disorder, ongoing malignant disease of any type that could influence the outcome of the treatment and might interfere with the evaluation of the study objectives).
- History of periodontitis staging III or IV grading B or C
- At least 2 sites with probing depth ≥ 6 mm or pockets of 5 mm with bleeding on probing in two different quadrants.
- Previous periodontal non-surgical treatment at least 3 months maximum 6 months.
- Availability for the 6-month duration of the study for an assigned subject.

Exclusion Characteristics

- Not willing to follow the agreed protocol.
- Presence of orthodontic appliances.
- Smokers more than 10 cigarettes per day
- Chronic obstructive pulmonary disease and asthma.
- Tumors or significant pathology of the soft or hard tissues of the oral cavity.
- Current radiotherapy or chemotherapy.
- Pregnant or lactating women.
- Current or past (within 3 months prior to enrollment) assumption of medications that may influence periodontal conditions and/or interfere with healing following periodontal treatment (i.e., corticosteroids, calcium channel blockers, systemic antibiotics, ...).
- History of allergy to Erythritol or chlorexidine.

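### The between-arm PERMANOVA cannot tell a change in the resident subgingival flora from arrival of the lozenge's own L. reuteri, because the plan does not remove those reads

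*Combined protocol and SAP*

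**What the plan says.** **Outcomes.** Study Outcomes, item c, lists "changes in microbial composition and proportion of sequences identified as *Lactobacillus reuteri* in the deepest residual pockets". That is two items: composition, and the L. reuteri proportion.

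**Exposure.** In section 1 (Study Design), Visit 2, the test lozenges carry two L. reuteri strains and are used twice daily for 3 weeks. For the other arm, "The patients of the control group will receive control lozenges without live bacteria". Visit 3 (T1) samples the same pockets at 3 weeks.

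**Community analyses.** Section 2, Sample processing, prepares one table: "The zOTU-table will be randomly subsampled to even depth". It then describes Shannon diversity, PCA on log2-transformed data, and the main test: "The statistical difference in microbial profiles between the study groups at each time point will be assessed using permutational analysis of variance (PERMANOVA"), with Bray-Curtis. Next, "Metagenomic biomarker discovery tool LEFSE will be used to identify microbial taxa that significantly discriminate the groups". Last, Bray-Curtis similarity between a patient's own visits is compared between arms. No taxon filter comes before any of these. The count scale for PERMANOVA (raw or log2) is not stated.

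**Lactobacillus.** The following paragraph says zOTUs of this genus "will be analyzed separately, in order to assess if the probiotic strains have established in the oral cavity". Sequences related to L. reuteri are flagged from a phylogenetic tree, and relative abundances are compared between arms at each visit. Nothing says that these zOTUs leave the community table.

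**The concern.** PERMANOVA is an omnibus test. Permuting arm labels over whole profiles tests whether the arms differ in any zOTU. Here one species is supplied to one arm by design. If it reaches the pocket, that null is false even when every resident taxon has the same distribution in both arms, and the p-value does not show which taxon was responsible.

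A significant result, above all at T1, could then be reported as an effect on the subgingival community when it only repeats the L. reuteri proportion item. The between-visit comparison works the same way: a test patient's T1 sample may hold a taxon that was absent at T0, which lowers similarity in that arm alone.

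**Working it through.** **1. The plan's own figure.** The documents give no power or error figure for the microbiological tests. Section 4 gives 20 patients per group for probing depth, which I use only as the number per arm. From its inputs, the SD of a patient mean is √(0.974² + 1.65²/7) = 1.157, and z = 1/(1.157 × √(2/20)) = 2.73. Power is 78.1% (normal) or 75.9% (t, 38 df), close to the stated 80%; the normal formula needs 21 per arm. The total follows from 40 × 1.1 = 44.

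**2. Simulation inputs.** From the documents: 20 v 20 patients, a 5% level, Bray-Curtis PERMANOVA, and live L. reuteri in one arm only. Assumed, because the documents are silent: one profile per patient, 5,000 reads, and a mean L. reuteri share *s* in the test arm (skewed between patients) and 0 in controls. Resident taxa come from the same Dirichlet distribution in both arms, at two dispersion settings. Set A has 150 resident taxa, 399 permutations and 1,000 trials per setting. Set B has 200, 199 and 300.

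**3. Formulas.** d = Σ|x − y| / Σ(x + y). SST = Σd²/40 over all pairs; SSW = Σd²/20 over within-arm pairs. The statistic is (SST − SSW)/SSW, and p is the proportion of label permutations at least as extreme.

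**4. Rejection with L. reuteri kept, raw counts, all test patients carrying it.** The last column also covers smaller repeat runs.

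| Mean share | Set A | Set B | All runs |
|---|---|---|---|
| 0 | 5% | 5–7% | |
| 0.1% | – | 6–7% | |
| 0.5% | 8–10% | – | 6–10% |
| 1% | 12–16% | 9–13% | 8–21% |
| 2% | 23–40% | – | 20–40% |
| 3% | 40–67% | – | |
| 5% | 77–94% | 77–96% | 74–96% |
| 10% | 99–100% | 99–100% | |

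At a 5% share in set B, arm explains 4.4–4.9% of the variation, against 2.5–2.6% at zero share.

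**5. Half of the test patients carrying it.** Set A holds the arm mean fixed and gives 7–9% at 1%, 11–18% at 2% and 35–53% at 5%. Set B gives carriers a mean of 5%, so the arm mean is 0.5 × 5% = 2.5%, and rejects 14–21%.

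**6. Log2(x + 1) counts, set B, all carrying.** Rejection is 27–32% at 0.1%, 92–97% at 1% and 100% at 5%. The reason is the weight of small counts. A 1% share is 50 reads, and log2(51) = 5.7. A taxon at, say, 20% is 1,000 reads, and log2(1,001) = 10.0. The ratio is 50/1,000 = 5% on raw counts but 5.7/10.0 = 57% on log2.

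**7. L. reuteri removed.** Set A: 3.8–6.1%. Set B, subsampled again to even depth after removal: 2.3–6.7% raw and 2.3–8.7% log2. The Monte Carlo standard error in set B is √(0.05 × 0.95/300) = 1.3 points.

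**8. The other analyses.**
- Between-visit Bray-Curtis: about 33–36% rejection at a 5% share. This also depends on how stable a patient's profile is between visits, which the documents do not give.
- Shannon, full table: 3.5–8.5% in 11 of 12 settings and 11.3% in the other, with no consistent rise with share.
- LEfSe's rank step on the L. reuteri zOTU: p = 0.076 with 3 of 20 test carriers and no control carriers, p = 0.038 with 4 of 20. Resident taxa tested alongside it (Mann-Whitney) are flagged at 4.6–5.0% for shares from 0 to 10%, which is nominal.

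**The case against.** **The outcome is composition, not resident flora.** A pocket that newly contains L. reuteri has changed composition, so against the outcome as worded these rejections are correct detections. This stands: they are not type I errors of the stated outcome. A reader might infer from the Introduction ("The influence of probiotics on pathogens flora can derive from three principal modes of action") that pathogen flora is the tested question. That sentence is general background; the stated Objective is probing depth, and the outcome list sets no such limit.

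**LEfSe.** A reader might infer that LEfSe misleads in the same way. It does not. It names each taxon, so an L. reuteri hit is visible as such, and resident taxa are still flagged at the nominal rate. Nor does the composition question go wholly unanswered, because the taxon-level results bear on it.

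**Separate analysis.** This could be read as taking Lactobacillus out of the table. But the stated purpose is colonisation, and no exclusion is written.

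**Existing safeguard.** The L. reuteri share will be compared at the same visits, so a careful reader is warned. That helps, but nobody can subtract its contribution from an omnibus p-value.

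**The share may be tiny.** Lozenges dissolve on the tongue, and samples come from inside the pocket after supragingival plaque is removed. On raw counts, a share below about 0.5% barely moves PERMANOVA. This stands as a limit on size.

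**Timing.** Intake ends at 3 weeks. Reads at 3 or 6 months would reflect persistence, which is a real feature of the community. The problem is therefore greatest at T1.

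**Conclusion.** The point holds for the omnibus PERMANOVA and, at larger shares, for the between-visit Bray-Curtis comparison. As written, a significant result cannot separate a change in resident flora from delivery of the dosed species.

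The size is uncertain. It ranges from negligible to near-certain rejection, depending on the pocket share, the fraction of test patients who carry the species, and the count scale; the documents settle none of these. The simulated rates also assume a sequencing depth, a resident community and one profile per patient, although two sites are sampled.

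The documents do not support extending the point to Shannon, or saying that the full-table test is invalid for composition as worded. The primary probing-depth analysis is untouched. This is a worthwhile, inexpensive clarification of a microbiological outcome.

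**What to change.** Add to section 2, Sample processing:

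> PERMANOVA and the between-visit Bray-Curtis comparison will also be run after removing the zOTUs flagged as L. reuteri-related. Removal applies to all samples in both arms and comes before subsampling to even depth. Any conclusion that the resident subgingival community differs between arms will rest on this filtered analysis; the full-table result will be reported alongside it. In LEfSe, L. reuteri features will be reported as colonisation, not as a change in resident flora.

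The order matters: removal after subsampling would leave the arms at unequal depth. Stating the count scale for PERMANOVA in the same place would also help. The L. reuteri proportion analysis stays as planned.

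The cost is one filter on zOTUs that the plan already flags and one more run of two analyses, with no new samples or visits. Any native L. reuteri is removed as well, by the same rule in both arms.

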CONFIDENTIAL AND PROPRIETARY

Information provided herein is the property of the University-Hospital of Brescia. Nothing herein is to be reproduced, published, or disclosed to others in any way without the prior expressed written permission of the University-Hospital of Brescia.

Title of Study: Clinical and microbiological efficacy of *Lactobacillus reuteri* in the supportive therapy of periodontitis: a 6 months Randomized Controlled Trial study.

Type of Study: Clinical and microbiological

Protocol No: PROTOCOL #PERIOPRO

Expected study start date: APRIL, 2020 (study initiation)

Study Location/Country: Brescia, Italy

Study Originator(s)/ Contact (name, phone, fax): [name], [name], [contact], email: [contact]

Test Products w/ PDM Numbers:

CE marked Medical Device to be used as an adjunct therapy to standard in patients with moderate to severe periodontal disease (Confidential information).

Study Title:	Clinical and microbiological efficacy of Lactobacillus reuteri in the supportive therapy of periodontitis: a 6 months Randomized Controlled Trial study.
Study sites:	[name] (lead site) University-Hospital of Brescia Brescia, Italy.
Study Phase:	IV.
Name of Medical Device:	GUM® Periobalance® (SUNSTAR SUISSE S.A. [name])
Objective:	The objective of the clinical study is to assess the efficacy of the addition of Lactobacillus reuteri in the supportive therapy of periodontitis in terms of reduction of PD (Probing Depth).
Patient Population:	44 periodontal patients, systemically healthy, male and female adults (18 – 75 years), with history of periodontitis grade B or C and stage III or IV, with at least 2 residual sites/pockets with probing depth ≥ 6 mm or pockets of 5 mm with bleeding on probing in two different quadrants.
Structure:	Parallel arms: Number of treatments: 1 (after a session of non-surgical supportive therapy one group takes probiotic (Lactobacillus reuteri) lozenges 2 times a day for 21 days, another group takes placebo lozenges 2 times a day for 21 days).
	Duration of study: 36 months.
Number of Centers:	One.
Blinding:	Patient, Examiner, Operator and Statistician -Blind.
Method of Patient Selection:	Periodontal pockets: at least 2 sites with probing depth ≥ 6 mm or pockets of 5 mm with bleeding on probing in two different quadrants.

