Total Sample Size:	44 adult subjects will be recruited (randomized) to participate in this study, with 40 expected to complete the study.
Primary Efficacy Variable:	Primary outcome measure will be the changing of PD in millimeters.

Clinical and microbiological efficacy of *Lactobacillus reuteri* in the supportive therapy of periodontitis: a 6 months Randomized Controlled Trial study.
PROTOCOL #PERIOPRO

Protocol Date: JAN 13, 2020

Protocol Approval

Signature Page

[name]
University-Hospital of Brescia, Italy

Date

ADDRESSES AND RESPONSIBILITIES

Addresses

Study Centres:	Section of Periodontics, School of Dentistry, Department of Surgical Specialities, Radiological Science and Public Health University of Brescia [name]
	[name] (Principal Investigator) [contact] Email: [contact]
Study coordinator:	[name] Section of Periodontics, School of Dentistry, Department of Surgical Specialities, Radiological Science and Public Health University-Hospital of Brescia Brescia, IT
Data Management & Monitoring:	[name] Section of Periodontics, School of Dentistry, Department of Surgical Specialities, Radiological Science and Public Health University-Hospital of Brescia Brescia, IT
Statistician:	[name] Unit of Biostatistics and Bioinformatics, Department of Molecular and Translational Medicine University of Brescia Brescia, IT
Microbiologist:	[name] Head of the Department of Preventive Dentistry Professor in Oral Microbial Ecology Academic Centre for Dentistry Amsterdam Vrije Universiteit Amsterdam and University of Amsterdam Amsterdam, the Netherlands

Responsibilities

The **principal investigator's** responsibilities are described in detail in ISO norm 14155:2011 for the clinical investigation of medical devices for human subjects.

The role of the principal investigator is to implement and manage the day-to-day conduct of the clinical investigation as well as ensure data integrity and the rights, safety and well-being of the subjects involved in the clinical investigation.

The principal investigator shall be qualified by education, training and experience to assume responsibilities for the proper conduct of the clinical investigation. In particular, the principal investigator is responsible for:

- qualification of investigation site;
- communication with Ethics Committee;
- compliance with Informed Consent process;
- compliance with Clinical Investigation Plan.

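### Lozenge packs carry a shared group letter and no patient-specific code, so one disclosed allocation could decode every letter seen; unique kit numbers would limit this at little cost

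*Combined protocol and SAP*

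**What the plan says.** The method is in section 2 (Treatments), under Blinding and Randomization. A staff member with no other part in the study generates the allocation and blinds the products by "labelling the packaging of these products with a letter indicating the treatment group". At inclusion, "the study medication will be handed out to the researcher according to group to which that patient will be assigned". The patient number serves to look up the group on the list; it is not described as the code on the pack. No kit number is mentioned.

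The same section says that the matching packs and lozenges "make the double-blinding of the researcher and patient possible", so the person who receives the packs is among those to be kept blind. The synopsis gives the blinding as "Patient, Examiner, Operator and Statistician -Blind".

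Packaging also comes back to the site. At Visit 3, three weeks after baseline, "the participants will be asked to return the empty packages of the study medication to examine the adherence" (section 1, Study Design). The examiner questions patients about side effects at that visit. PD is charted at screening, before randomisation, and again at 3 and 6 months.

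On numbers, the synopsis states: "44 adult subjects will be recruited (randomized) to participate in this study, with 40 expected to complete the study". The Study Population section adds that patients excluded for major deviations "will be replaced to guarantee that the sample required for the analysis (40) is reached".

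**The concern.** A label shared by a whole arm ties the blinding of all its patients together. With two arms, decoding one letter decodes the other by elimination. A disclosure that ought to concern one patient then concerns everyone whose letter the informed person has seen or will see. Even with no disclosure, a shared letter lets staff sort patients into two groups.

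This matters because the primary outcome is a manual probe reading rounded to the nearest millimetre, which depends on the reader's judgement. Knowing one patient's arm can barely move a group mean, whereas knowing the whole allocation can. Recruitment is rolling, so letters decoded early would also apply to patients enrolled later.

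**Working it through.** The plan gives no figure for this point, so there is none to reproduce. The check has three steps.

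**1. How far one disclosure spreads.** Inputs: 44 randomised (synopsis, Total Sample Size) and two arms (synopsis, Structure). Assumptions: equal arms, and a person who sees every letter.

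- One letter per arm: one letter is decoded directly and the other by elimination, so up to 44 of 44 allocations are revealed.
- Unique code per patient: 1 of 44.
- Several letters per arm (not described, shown for range): patients sharing a letter = 44/(2k) for k letters per arm. This gives 44/4 = 11 for k = 2 and 44/8 = 5.5 for k = 4.

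Replacements that are randomised would raise the maximum above 44. A leak of the whole list reveals everyone under any scheme.

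**2. Who could meet the letters.** Section 2 puts lettered packs in the hands of the researcher. Section 1 brings empty packages back at 3 weeks, before both follow-up PD chartings, at a visit where the examiner also has a task. Exposure of site staff is therefore plausible. No section says that the researcher is the examiner, or who takes in the returned packages.

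**3. Scale of a possible effect on PD.** Inputs from section 4 (Sample size determination): an average of 7 sites per patient, 20 patients per group and an expected difference of 1 mm. Because readings are rounded to whole millimetres (section 1, item i), 1 mm is the smallest recordable step. A 1 mm step at one site moves:

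- a patient's mean by 1/7 = 0.14 mm;
- the arm mean by 1/(7 × 20) = 0.007 mm if it occurs in one patient;
- the arm mean by m/(7 × 20) mm if it occurs in m patients of that arm.

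Only readings still to be taken can be affected. Baseline PD is safe because it precedes randomisation. For the 6-month reading, assume 40 completers, even accrual over the estimated 12 months of recruitment (section 1, item d) and equal arms. The number of completers unread at disclosure month t is 40 for t ≤ 6, and 40 × (18 − t)/12 for 6 < t ≤ 18.

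| Disclosure month | Unread, both arms | Unread per arm (m) | Arm-mean shift, m/140 |
|---|---|---|---|
| 6 or earlier | 40 | 20 | 0.14 mm |
| 9 | 30 | 15 | 0.11 mm |
| 12 | 20 | 10 | 0.07 mm |
| 15 | 10 | 5 | 0.04 mm |
| 18 | 0 | 0 | 0 mm |

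The 3-month reading closes three months sooner: 40 × (15 − t)/12 for 3 < t ≤ 15, which is 30 unread at month 6, 10 at month 12 and 0 at month 15.

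The step size is arbitrary. The table shows how a shared letter scales an effect and how that effect shrinks with time; it does not predict bias.

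**The case against.** The strongest reply is that no error has been shown. The labeller is independent, access to the list is restricted until the last final examination and CRF verification, the jars are identical and opaque, and the lozenges match in taste, texture and appearance. The obvious trigger, a single-patient unblinding, is hypothetical: no individual code-break procedure is described, and the chance of a disclosure cannot be estimated from the documents. The number of letters is unstated, and the count of 44 depends on it. Sorting patients by an undecoded letter gives bias no known direction.

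Most of this stands, and it limits the weight of the point. It does not remove the point. The safeguards lower the chance of a disclosure, but none limits how far one spreads, and identical jars do not hide a letter on the label.

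Three stronger readings are tempting, and the documents do not support them:

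- **The examiner is unblinded.** A reader might infer this from the return of packages at a visit where the examiner has a role. The text does not say that the examiner handles the packages or sees the letters, and the synopsis declares the examiner blind.
- **The letter reaches examiners through the CRF.** Section 7 (Data Management) has examiners extract CRF data, while section 1, item j, gives entry to a data entry staff member. Neither says that the letter is recorded on the CRF, so this route is speculation.
- **A 0.14 mm arm shift applies whenever the code is broken.** It requires all 20 patients of the arm to be unread, which under even accrual means disclosure by about month 6.

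**Conclusion.** The point holds as a minor design improvement. The stated method lets one disclosed allocation expose up to all 44 patients, where a patient-specific code would expose 1. This rests on one letter per arm and on a person who has seen the letters. The first is the literal reading; the second is plausible for site staff but not documented for the examiner.

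The possible effect on PD is confined to untaken readings and is small on the illustration used. At most it is about one-seventh of the planned 1 mm difference, half of that by month 12, and nothing for the 6-month reading by month 18. Those figures also assume 40 completers and even accrual.

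A reader might conclude that the blinding has failed or will fail. The documents show neither: the plan has real safeguards, and no disclosure is documented or expected.

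**What to change.** In section 2, Blinding and Randomization, replace the group letter with a unique kit number for each patient. The same independent staff member should assign the numbers from the randomisation list, prepare spare numbered kits for the replacements allowed under Study Population, and keep the number-to-arm key. Packs should be selected by kit number, and no group letter should appear on packs or returned packages. The statistician can still receive a masked group code in the dataset.

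The cost is relabelling about 44 or more sets of jars, picking packs by number instead of by group, and a short protocol revision. It adds no visits or patients.
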